In addition, majority of cases of DILI in the published clinical and genetic studies have been enrolled retrospectively; hence, the data set is reliant on clinical investigations and the setup of health services which are incomplete. In addition, the majority of the studies have used healthy populations as control groups (rather than those exposed to the drugs). Despite the discovery of genetic factors such as the association of specific HLA genotype with DILI, a low positive predictive value of the genotype in predicting DILI is limiting its use in clinical practice [8,9]. Age, smoking, metabolic syndrome, co-morbidity and other yet unidentified factors may generate an environment of oxidative stress that contributes to DILI. Therefore, we need 'in-depth phenotyping' together with data from an exposed control group to develop refined algorithms incorporating drug-related factors, host genetic and environmental risk factors that would enable us to pre-empt DILI. Deeply phenotyped cohorts with biological samples are essential for the development and validation of novel diagnostic/ prognostic markers [10].

STUDY OBJECTIVES AND PURPOSE

Purpose

The purpose of this study is to set up an international interdisciplinary consortium to obtain a better understanding of the mechanisms underlying drug-induced liver injury (DILI) and to develop methods of preventing DILI and its consequences. The consortium including the clinicians and scientists from European countries covering a wide area of expertise will allow the development of mature hypotheses that can be tested using a robust study design. The consortium will facilitate the development of strong translational research proposals based on our hypothesis.

Primary Objective

To, collect, store and catalogue biological samples and clinical data, to form a large international patient/control cohort available for subsequent detailed analysis by consortium members which can also be used in current and future epidemiologic and mechanistic studies.

Proposal Aims:

We hypothesise that the severity of DILI is determined by factors that modulate cellular response to oxidative stress and the transition of adaptive response to the development of serious DILI can be recognised by a combination of markers that reflect the balance

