Causal DILI agents will be classified according to World Health Organisation (WHO) anatomical therapeutic chemical (ATC) classification system. Associated diseases will be classified according to the WHO tenth edition of the international classification of diseases, ICD-10.

STUDY POPULATION

Recruitment will be over a nine year period (up to April 2024).

-For suspected DILI patients : 3-7 visits, (each visit lasting for up to 30mins). Each patient will be in the study for up to 6 months duration.

Follow-up: Each patient will have a clinical follow up until the event resolves or 12 weeks after the first event whichever occurs later. We will also follow-up outcomes in clinical notes over a 10 year period after recruitment where consent is given.

Enrolment:

We expect to enrol each case at the earliest opportunity possible, following the suspected DILI event (or AIH event) (up to a maximum of 8 weeks from diagnosis) when research team anticipates that they will meet inclusion criteria below. Each patient will be followed from the identification of hepatotoxicity until normalization of the analytical liver profile.

Enrolment will begin once a patient has been clinically diagnosed with suspected DILI and gives consent to take part in the study. In all instances the visit schedule should be adapted to routine hospital procedures in order to facilitate patient participation as well as avoid additional hospital costs (see diagram below).

- Control participants (on medication or untreated but without DILI symptoms): A

single study visit of up to 30 minutes duration. Controls will be required to provide biological samples, demographic and medical data will also be collected.

Study Duration:

Enrolment will end at 9 years from the start of the study (Apr 2024) or once the recruitment target has been met, whichever is soonest.

INCLUSION CRITERIA

All patient and control groups:

- Aged 18 years and over
- Able to give written informed consent OR consent provided by consultee (personal or nominated) for potential participants with suspected DILI who lack capacity to give written informed consent.

A. Suspected DILI Patients:

Adults diagnosed with suspected acute DILI (within 8 weeks of diagnosis) and meeting the following criteria will be included:

1. Meets one of the following analytical thresholds at enrolment (visit 1)

- alanine transaminase (ALT) exceeding 5 times upper limit of normal (ULN) OR
- alkaline phosphatase exceeding 2 times ULN OR

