Healthy Control Group:

Adults who are exposed to the same drugs (as those responsible for DILI) without developing DILI will be identified. The Chief Investigator will access hospital pharmacy databases to identify patients taking specific drugs of interest. Then patients exposed to particular drugs without developing DILI will be invited to participate in the study as a control group. In the UK this will be done at the Nottingham site initially, extending to other sites where appropriate.

We will also advertise through BRC website (https://nddcbru.org.uk/pro-euro-dili) (appendix 2 shows screen shot) and social media pages (Facebook and Twitter) to invite people who have taken the particular drugs to contact us if they are interested in participating in the study (as control group).

A proportion of patients who are suspected to have DILI and enrolled as cases will be found to have an alternative explanation for their clinical manifestation found on subsequent investigation. The data and samples taken from these patients will be retained in the study and termed 'symptomatic controls' for analysis purposes. Sample and data collection will be continued in line with confirmed DILI participants.

INFORMED CONSENT

The process for obtaining participant informed consent will be in accordance with the REC guidance, and Good Clinical Practice (GCP) and any other regulatory requirements that might be introduced. Since DILI symptoms are acute and patients often present in emergency departments with sudden onset of severe symptoms, a long period (e.g. 24h) to consider consent is often difficult to provide in order to recruit patients while symptomatic and without asking patients to make additional hospital visits. Therefore, where appropriate, patients will be given a reasonable time period (ideally1 hour without disturbance), to read the patient information sheet and consider enrolment before being approached for consent by the research team. Appropriate steps will be taken to ensure that the patient is able to discuss participation in the study with those not involved in the research. The investigator or

Pro-Euro-DILI Registry Protocol Page 15 of 32

their nominee and the participant or other legally authorised representative shall both sign and date the Consent Form before the person can participate in the study.

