In the current study we will be performing venepunctures for blood sampling. So, we will report major bleeding leading to hypotension, drop in Hb, requirement of resuscitation, transfusion or hospital admission will be reported as adverse events. All SAEs should be

reported to the **Research Ethics Committee** where in the opinion of the Chief Investigator, the event was:

- 'related', i.e. resulted from the administration of any of the research procedures; and
- 'unexpected', i.e. an event that is not listed in the protocol as an expected occurrence

Reports of related and unexpected SAEs should be submitted within 15 days of the Chief Investigator becoming aware of the event, using the COREC SAE form for non-IMP studies.

Local investigators should report any SAEs as required by their Local Research Ethics Committee and/or Research & Development Office.

Sponsor Contact Details for SAEs:

1. email to

Any queries please contact a member of staff in the Research & Innovations department:

Telephone:

ASSESSMENT AND FOLLOW-UP

Follow-up: There are no protocol-driven follow up visits beyond Day 180 (Visit 5).

End of the Study

This study involves the collection and storage of data and tissue. We will be seeking consent to collate, store and use samples and data for a minimum of 10 years.

Collated biological samples will be stored in a REC-approved tissue bank located on HTA licenced premises for subsequent analysis by members of the consortium and collaborators in future projects for at least 10 years.

Data collection

Data to be collected from each patient are described in Appendix 1. Data to be collected from controls will follow the same protocol, with the exclusion of information directly relating to a DILI episode.

The PI in each collaborating hospital will be responsible for entering the corresponding patient/control data into the Pro-Euro DILI Registry database (developed by Coresoft Clinic S.L, http://www.coresoft.es), available online. Tutorials on data entry and database implementations will be organized by the co-ordinating centres (Málaga and Nottingham) during the pilot phase and later if required.

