All routine laboratory analysis will be done by appropriate hospital as part as normal patient care. Blood will be processed for storage of serum and plasma as outlined in the SOP. Data and all appropriate documentation will be stored for a minimum of 25 years after the completion of the study, including the follow-up period.

We will collate detailed and comprehensive data using an electronic case report form (eCRF) to achieve in-depth phenotyping.

The procedure for data removal in the event of withdrawal of consent is described on pg 25.

Statistical Analyses

Researchers will be blinded to patient type/group being investigated – samples will be anonymized and labelled only with study ID code. Study groups will be compared using T-tests and non-parametric testing to identify biomarkers which distinguish DILI.

STUDY MANAGEMENT

The day-to-day management of the study will be co-ordinated through Nottingham Digestive Diseases Centre and NIHR Nottingham Biomedical Research Centre.

SPONSOR

Nottingham University Hospitals NHS Trust will act as the main sponsor for UK based sites for this study. Delegated responsibilities will be assigned to the NHS trusts taking part in this study.

FUNDING

Participant stipends and payments

Participants will not be paid to participate in the study. Travel expenses will be offered for any hospital visits in excess of usual care.

AUDITS

The study may be subject to inspection and audit by Nottingham University Hospitals under their remit as sponsor and other regulatory bodies to ensure adherence to GCP and the NHS Research Governance Framework for Health and Social Care (2nd edition).

STUDY CONDUCT

Study conduct will be subject to systems audit for inclusion of essential documents; permissions to conduct the study; CVs of study staff and training received; local document control procedures; consent procedures and recruitment logs; adherence to procedures defined in the protocol (e.g. inclusion / exclusion criteria, timeliness of visits); accountability of study materials and equipment calibration logs.

STUDY DATA

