Appendix 1. Overview of Patient assessment schedule

*Autoantibodies: antinuclear (ANA), antismooth muscle (ASMA), antimitochondrial (AMA) and liver kidney microsomal type 1 (LKM-1)

**Repeat autoantibody screening if positive in week 1

[#] For 'past DILI' patient group and control groups there will be just a single visit, visit 1 -clinical blood tests will not be done.

[§]Only if patient is hospitalized, ^{§§}Only if patient has elevated liver profile values at visit 3, ^{§§§}Only patients with elevated liver profile values at previous visit (visit 4) Appendix 2 Histopathological terms to be used for liver biopsy reports in patients with suspected drug-induced hepatotoxicity.

CODE	DESCRIPTION
1	HEPATOCELLULAR NECROSIS
11	FOCAL NECROSIS
12	BRIDGE NECROSIS
13	ZONAL NECROSIS
14	MASSIVE NECROSIS
2	STEATOSIS / FATTY LIVER
21	ACUTE STEATOTIC CHANGES
22	STEATOHEPATITIS (NASH)
3	GRANULOMATOUS REACTION
4	ACUTE COLESTASIS
41	CHOLESTASIS WITHOUT HEPATITIS
42	CHOLESTASIS WITH HEPATITIS
43	CHOLESTASIS WITH DUCTAL LESION
5	CHRONIC CHOLESTASIS
51	PROLONGED CHOLESTASIS
52	DUCTOPENIA ("VANISHING BILE DUCT SYNDROME")
53	SCLEROSING CHOLANGITIS
6	CHRONIC HEPATITIS
61	CHRONIC ACTIVE HEPATITIS
62	HEPATIC FIBROSIS AND CIRRHOSIS
7	VASCULAR ALTERATIONS
71	SINUSOIDAL DILATATION (FLARING) AND PELIOSIS
72	NON-CIRRHOTIC PORTAL HYPERTENTION
73	OBSTRUCTION TO THE VENOUS HEPATIC FLOW (Budd-Chiari
74	OTHERS
8	HEPATIC TUMORS
81	HEPATOCELLULAR ADENOMA
82	HEPATOCELLULAR CARCINOMA
83	OTHER CARCINOMAS
84	ANGIOSARCOMA
9	UNSPECIFIC CHANGES

Appendix 3

Drug-induced Liver Injury

Introduction to **DILI**

- DILI is an unexpected injury to the liver that can be caused by prescribed medications, over-the-counter medications, recreational drugs and supplements.
- Some drugs such as paracetamol are known to be harmful to the liver in high doses but other drugs, taken at a normal dose can unpredictably damage the liver of certain people.
- DILI is a rare, unpredictable disease and it is not known why certain individuals are more likely to develop drug-induced liver injury than others. This can be life-threatening.
- · Specific genetic risk factors can contribute to individual susceptibility but they do not fully explain why people get DILI.

Study Aims

To create a unique International Biobank resource to enable research into the causes and characteristics of drug-induced liver injury (DILI) so that new, non-invasive diagnostic tests can be developed

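### The protocol admits untreated controls in one section and requires drug-exposed controls in another, and does not say that only exposed controls enter the DILI comparison

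*Protocol*

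**What the plan says.** The text on asymptomatic controls is spread over several sections of the protocol.

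- **Study Population, Enrolment:** "Control participants (on medication or untreated but without DILI symptoms" attend one visit. Exposure is optional here.
- **Identifying Participants, Healthy Control Group:** "Adults who are exposed to the same drugs (as those responsible for DILI) without developing DILI will be identified". Exposure is required here. There are two recruitment routes: hospital pharmacy databases, and advertising "to invite people who have taken the particular drugs to contact us".
- **Rationale for current study:** earlier work is faulted because "the majority of the studies have used healthy populations as control groups (rather than those exposed to the drugs". The stated need is for deep phenotyping "together with data from an exposed control group to develop refined algorithms".
- **Inclusion Criteria:** the only criteria that reach controls are age and consent. Drug exposure and the ALT, ALP and bilirubin thresholds are listed for suspected DILI patients.
- **Data collection:** "Data to be collected from controls will follow the same protocol, with the exclusion of information directly relating to a DILI episode". Appendix 1 places drug history, covering at least the past six months, at visit 1.
- **Appendix 1, footnote:** for "control groups there will be just a single visit, visit 1 -clinical blood tests will not be done".
- **Statistical Analyses:** "Study groups will be compared using T-tests and non-parametric testing to identify biomarkers which distinguish DILI". No division of controls by exposure is mentioned.

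**The concern.** An untreated person meets the Enrolment description and fails the Healthy Control Group description, so two sites could follow the protocol and recruit different kinds of control. Suspected cases have all taken a drug (inclusion criterion 2). A comparison of cases with a mixed control group therefore contrasts DILI with no DILI and, in part, drug and its indication with neither. A marker that responds only to the drug or to the disease being treated would then look like a marker of DILI. This is the weakness that the Rationale sets out to avoid.

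A second, smaller question is how a control is known to be free of DILI. Case status rests on laboratory thresholds, and the Mild severity grade requires no symptoms. Absence of symptoms therefore cannot by itself exclude DILI as the protocol defines it, and no clinical blood tests are done on controls.

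**Working it through.** The protocol gives its sample size estimate as N/A, so it has no figure to reproduce. What follows is an illustration.

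**Inputs**
- Confirmed cases: 300 (Primary endpoint).
- Controls: 300 or 100 (assumed; no number is legible in the available text).
- Share of controls untreated, u: 10%, 25% or 50% (assumed).
- Shift in a marker due to exposure or indication alone, D: 0.3 SD, with a range of 0.2 to 0.5 SD (assumed).
- Test: two-sided 5%, normal approximation (assumed; the protocol states no significance level).

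**Step 1. Spurious difference.** If the marker has no relation to DILI and the control group is pooled, cases differ from controls by u × D. For D = 0.3 this is 0.03, 0.075 and 0.15 SD.

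**Step 2. Standard error, in SD units.** SE = √(1/300 + 1/n).
- n = 300: √(2/300) = 0.0816.
- n = 100: √(1/300 + 1/100) = 0.1155.

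**Step 3. False-positive rate.** P = 1 − Φ(1.96 − b) + Φ(−1.96 − b), where b = u × D / SE. For u = 50% and n = 300, b = 0.15/0.0816 = 1.84 and P = 45.1%.

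| Untreated share u (D = 0.3) | 300 controls | 100 controls |
|---|---|---|
| 0% | 5.0% | 5.0% |
| 10% | 6.6% | 5.8% |
| 25% | 15.1% | 10.0% |
| 50% | 45.1% | 25.5% |

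With D from 0.2 to 0.5 and 300 controls, the rate runs from 9.4% to 33.4% at u = 25%, and from 23.2% to 86.5% at u = 50%. With 100 controls and u = 50%, it runs from 13.9% to 58.1%. If all controls in the comparison are exposed, the difference from this source is zero and the rate returns to 5%.

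**Step 4. Undetected DILI among controls.** The highest incidence cited in the Background is 19.1 per 100,000 per year, and 300 × 0.000191 = 0.06 controls. That is a population rate and may be too low for drug-exposed people, so assume a share q of 1% to 5%, which is 3 to 15 of 300. If such controls have the case mean, a true difference of 0.25 SD shrinks to 0.25 × (1 − q), that is 0.2475 or 0.2375 SD. Power with 300 per group falls from 86.5% to 85.8% or 82.9%.

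**The case against.** The strongest defence is that the harm needs two things the protocol does not state: that untreated controls are actually recruited, and that they are pooled with exposed ones.

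- Both recruitment routes in the Healthy Control Group section look for people who take or have taken the drugs of interest. No route to untreated people is described.
- The protocol speaks of control groups in the plural. The Enrolment line mainly describes visit burden, so it may be an umbrella for more than one group. Group formation may also be set out in a statistical analysis plan that is not at hand.
- Untreated could mean not currently treated rather than never exposed.
- Suspected cases later adjudicated as non-DILI serve as symptomatic controls. They are drug-exposed, have liver tests at enrolment and are analysed as a separate group.
- Drug history is collected on controls, so exposed and untreated people can be told apart afterwards.

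Most of this stands, and it limits the point. A reader might infer that the study will repeat the flaw of earlier work, or that false-positive rates of 45% or more are to be expected. The documents support neither: nothing in them suggests that half the controls will be untreated, and at 10% untreated the rate barely leaves 5%. A reader might also infer that freedom from DILI is ignored. In fact it is a stated condition of selection; what is missing is a way to establish it. The footnote excludes clinical blood tests for controls but not the use of existing results or stored serum.

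The defence does not remove the conflict. Who may enter as a control is a protocol matter, the two descriptions disagree, and the symptomatic controls answer a different question from the exposed, unaffected controls that the Rationale calls for.

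**Conclusion.** The protocol describes its asymptomatic controls in two incompatible ways and does not reserve the DILI comparison for exposed controls. The risk is conditional on untreated controls being enrolled and pooled. Under the assumptions above (300 controls, 0.3 SD exposure effect), the false-positive rate for a marker unrelated to DILI is about 7%, 15% or 45% at 10%, 25% or 50% untreated. The direction of the bias follows from the text; its size depends on u, D and the number of controls, none of which the protocol gives.

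The missing check of DILI-free status is real but minor. Even an assumed 5% of undetected DILI lowers power by under 4 percentage points (86.5% to 82.9%) for a 0.25 SD difference.

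This should be fixed but is not critical. The primary endpoint is the acquisition of samples and data, and the exposure split can be recovered from recorded drug history. What cannot be recovered is any shortfall in exposed controls if places are filled by untreated people.

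**What to change.** 1. Reconcile Enrolment with Healthy Control Group by naming drug-exposed controls and untreated controls as separate groups, each with its own eligibility line. Untreated controls need not be dropped, since they can help to separate drug effects from DILI effects.
2. State in Statistical Analyses that the DILI-versus-control comparison uses exposed controls only, stratified by causal drug or by ATC class where numbers allow. The protocol already classifies causal agents by ATC and collects drug history; date of last intake before sampling should be recorded explicitly.
3. As a secondary step, confirm control status from an existing routine ALT, ALP and bilirubin result or, where there is none, by assay of stored serum. Apply the study's own thresholds before the blinding to group is lifted.

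The cost is a wording amendment, fewer controls in the main comparison and, where no routine result exists, three routine assays per control.
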